## 7.4 Safety Population

The **Safety Population** will include all subjects who have received one dose of Study Treatment. This population will be used for the analysis of safety parameters or measurements. This population will include the subjects from the single arm, non-randomized, open-label phase that received leronlimab.

#### 8. DATA CONVENTION AND RELATED DEFINITIONS

#### 8.1 Baseline Definition

For all parameters, baseline will be defined as the last available value prior to randomization.

## 8.2 Duplicate Data

For unplanned duplicate data within a protocol-specified visit, the last measured value will be used for the analysis. If it is not possible to identify the "last measured value" the average of the duplicate values will be used.

No data will be excluded. All collected data will be listed.

### 8.3 Handling of Missing Data

Every effort will be made to obtain required data at each scheduled evaluation from all subjects who have been randomized to minimize missing data. However, in the event when there is missing data the following imputation methods will be used.

For efficacy evaluations, multiple imputation methods will be used to handle missing data. This imputation method is a robust method to impute missing measurements. The method for imputing variables is available in SAS PROC MI for both monotone and arbitrary missing data patterns and will be implemented with the PREDICT MEAN MATCHING option. Each imputation model will include the stratification factor as a covariate in the model. The multiple imputation is used for subjects that have some baseline and post-baseline data, i.e., if a subject is missing all pre and post baseline data, no data will be imputed.

### 8.3.1 Multiple Imputation for Continuous variables

If the missing data point is **continuous** in nature with **monotone** pattern, predictive mean matching (PMM) method will be used in the model.

If the missing data point is **continuous** in nature with **arbitrary** pattern, a fully conditional specification (FCS) using the predictive mean matching (PMM) method with joint distribution for all variables will be used.

#### 8.3.2 Multiple Imputation for Categorical variables

If the data point is categorical in nature with monotone pattern, logistic method will be used in the model.

If the data point is categorical in nature with arbitrary pattern, a fully conditional specification (FCS) using logistic regression approach with joint distribution for all variables will be used.

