## Follow Up Period (2 and 4 weeks after EOT± allowed windows)

Follow-up visits will be performed at 2 weeks (V6) and 4 weeks (V7) after the End of Treatment (EOT) visit. In order to ensure the safety of subjects and site staff, follow-up visits can be conducted as telephone or video contact visits. The following assessments will be performed at V6 and V7 visit: review of adverse events and concomitant medications, physical examination, vital signs, clinical status – ordinal scale assessment (V6 only), nasopharyngeal swab sample collection, mortality status, and blood collection for routine serum biochemical, hematologic, coagulation and urine laboratory assessments (V7 only). If V7 is a telephone/video visit, the scheduled blood sample collection will not be performed. In such cases, missed blood sample collection will not be captured as protocol deviation.

**Note**: During visits conducted at the study clinic, subjects and site personnel will use appropriate protective gear (e.g., masks, gloves) to prevent the spread of the infection. If the subject is discharged from the hospital prior to Visit 7 (Day 42), scheduled study visits can be conducted by a visiting nurse (or trained site staff) at the subject's home to mitigate the risk of spreading COVID-19.

During visits conducted at the subject's home, the visiting nurse (or trained site staff) will administer study drug (if applicable), monitor subjects for safety, perform blood draw, and all other assessments related to study outcomes measures. All procedures (except chest radiograph or CT scan) listed under the schedule of assessments can be performed by visiting nurse at visits taking place in the subject's home.

Table 2-1: Schedule of Assessments

Table 4-2: Schedule of Assessments

Procedure/Assessments	Screening Visit	T I I PAREMENT Place						Follow-Up	
Visit	VI	V2 [ (Pre-Rx)	17] (Post-Rx)	V3	V4	V5 (EOT)	V6	V7	
Day		Day	0	Day 3	Day 7	Day 14	Day 25	Day 42	
Window Period		Within 7 days of Vis		3(±1) days after V2	7(±1) days after V2	7(±1) days after V4	14(±3) days after EOT Visit	28(±3) daya after EOT Visit	
Informed Consent [1]	Х								
Eligibility Evaluation [2]	X								
Subject Demographics	X								
Medical History [3]	X								
Physical Examination	X	X		X[4]	X[4]	X	X[4]	X [4]	
Vital Signs [5]	X	X	X	X	X	X	X	X	
Clinical Status - Ordinal Scale Assessment	Х	X		X	X	X	X		
PaO2/FiO2, if intubated	х	X		X	X	X			
Pulse oxygen saturation (SpO2)	Х	X		X	Х	Х			

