## 3.2 Secondary Endpoints

The secondary efficacy endpoints for the study are:

- Proportion of patients achieving a category of 6 or higher at Days 14 and 28 (on a 7 point ordinal scale).
- All-cause mortality at Day 14
- Change in clinical status of subject at Days 14 and 28 (on a 7 point ordinal scale)
  - A 7-category ordinal scale of patient health status ranges from: 1) Death; 2) Hospitalized, on invasive mechanical ventilation or extracorporeal membrane oxygenation (ECMO); 3) Hospitalized, on non-invasive ventilation or high flow oxygen devices; 4) Hospitalized, requiring supplemental oxygen; 5) Hospitalized, not requiring supplemental oxygen; 6) Not hospitalized, limitation on activities; 7) Not hospitalized, no limitations on activities.
- Length of hospital stay (days)

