# 9.2.1 Primary Efficacy Endpoint

The primary endpoint for the study is all-cause mortality at Day 28. All-cause mortality at Day 28 will be summarized. The estimated difference in mortality rates along with 95% confidence interval and p-value will be calculated using Logistic Regression adjusting for stratification factors (Ge et al. 2011).

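### Imputed clinical status is not tied to recorded vital status, so a subject known to be alive can be imputed as Death on the ordinal secondary endpoints

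*SAP*

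**What the plan says.** Protocol 8.9.3 leaves the details of multiple imputation to the SAP. SAP 8.3 sets a wide scope: "For efficacy evaluations, multiple imputation methods will be used to handle missing data". It names one covariate: "Each imputation model will include the stratification factor as a covariate in the model". SAP 8.3.2 then gives two branches for categorical variables. For a monotone pattern the text is "pattern, logistic method will be used in the model". For an arbitrary pattern it is a fully conditional specification "using logistic regression approach with joint distribution for all variables will be used"; which variables are meant is not stated.

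The scale is defined in SAP 3.2: "A 7-category ordinal scale of patient health status ranges from: 1) Death". Two secondary endpoints use it at Days 14 and 28: the proportion at category 6 or higher, and the change in status. They are the first two listed in SAP 9.2.2, the section that SAP 8.4 cites for the order of the fixed-sequence tests. Mortality is analysed separately. SAP 9.2.1 states "The primary endpoint for the study is all-cause mortality at Day 28", and Day 14 and Day 42 mortality follow as secondary and exploratory endpoints.

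The follow-up text of SAP 2.2 lists "ordinal scale assessment (V6 only), nasopharyngeal swab sample collection, mortality status" for V6 and V7. The scale therefore stops at V6 (Day 28), while the schedule of assessments records mortality status at V5, V6 and V7.

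The only SAP rule on how a death enters another endpoint is 8.7.4, which covers length of stay and duration of mechanical ventilation.

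**The concern.** Death on this scale is a recorded fact whenever vital status is known. It should not be drawn from a model for a subject later seen alive. The schedule makes such subjects possible. Someone who misses V6 but is alive at V7 was alive at Day 28 and has no Day 28 category. Someone who misses V5 but is alive at V6 was alive at Day 14 and may have no Day 14 category. The SAP does not confine either subject to categories 2 to 7.

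Nor does it require agreement within a completed dataset. Nothing makes imputed death absorbing across Days 14, 28 and 42, and nothing makes the imputed category agree with the mortality value. At stake are impossible values in the two ordinal endpoints that stand first in the secondary testing order, and completed data in which one subject is alive for one endpoint and dead for another.

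**Working it through.** **Planning figures.** From SAP 4: Day 28 mortality 45% on placebo and 30% on leronlimab, two-sided 0.05, 80% power, 2:1 allocation. The unpooled Z-test gives a placebo group of (1.960 + 0.842)² × (0.45×0.55 + 0.30×0.70/2) / 0.15² = 122.97, so 123, and 369 in total. This matches the plan, and the concern disputes no stated figure.

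**Assumptions not in the documents.** A share m of survivors misses only the V6 category (5%, with 10% as a variation). Of those alive, 78% are at category 6 or 7. Vital status is left out of the imputation model, and missing categories are drawn from the observed seven-category distribution, by arm or pooled. This is a deliberate upper bound for the assumed missingness.

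**Day 28, m = 5%.**

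1. Known survivors without a category: 246×0.70×0.05 = 8.61 (leronlimab) and 123×0.55×0.05 = 3.38 (placebo), together about 12.
2. Death share among observed categories. By arm: 0.30/(0.30 + 0.70×0.95) = 0.311 and 0.45/(0.45 + 0.55×0.95) = 0.463. Pooled: 129.15/(129.15 + 239.85×0.95) = 0.362.
3. False deaths per dataset. By arm: 8.61×0.311 + 3.38×0.463 = 2.68 + 1.57 = 4.2. Pooled: 11.99×0.362 = 4.3. Simulation gave 4.3 to 4.4.
4. Understatement of category 6 or higher. A false death counts the same as categories 2 to 5 on this endpoint, so it matters only in the 78% of cases where the draw should have been 6 or 7. By arm: 2.68×0.78/246 = 0.85 point and 1.57×0.78/123 = 0.99 point. Pooled: 0.99 and 0.78 point.
5. Shift in the arm difference: 0.99 − 0.85 = 0.14 point by arm and 0.99 − 0.78 = 0.21 point pooled, in opposite directions. The contrast implied by the assumptions is 0.78×(0.70 − 0.55) = 11.7 points.

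**Day 28, m = 10%.** The same steps give an understatement of 1.76 and 2.04 points by arm (shift 0.28), and 2.044 and 1.606 points pooled (shift 0.438). The shift stays at 0.5 point or less.

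**What vital status in the model changes.** Two cumulative-logit simulations were run (60 replicates, 390 subjects, 20 of them known alive with a missing category; the category distributions are assumptions).

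| Missing item | Predictors besides arm and stratum | Expected false deaths among the 20 |
|---|---|---|
| Day 28 category | none | 6.9 (range 5.4 to 8.7) |
| Day 28 category | Day 28 vital status | about 0 (order 1e-6) |
| Day 14 category | Day 28 category | 1.0 (range 0.3 to 2.1) |
| Day 14 category | Day 28 category and alive indicator | 0.8 (range 0.2 to 1.6) |

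The first row agrees with a direct count for 5% of all 390 subjects: 13×0.30 + 6.5×0.45 = 6.8. Joint modelling therefore nearly removes the Day 28 problem and leaves a smaller one at Day 14. A hard restriction gives zero in every row by construction.

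**The case against.** The strongest reply is that the arbitrary-pattern branch models all variables jointly. Read naturally, that includes mortality status, so it is not true that imputation has no link to vital status. This stands: a reader might infer a complete disconnection, and the SAP does not support that. But a predictor brings an association, not a constraint. The phrase is undefined, a residue remains at Day 14, and the monotone branch, which fits a subject missing only the last ordinal visit, does not contain it. That branch is silent on mortality; it does not exclude it.

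A reader might also expect a perfect predictor (alive at Day 42) to do harm by separating the logistic fit. No failed fit was shown. Separation of this kind pushes the imputed probability of Death towards zero, which is the wanted result.

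The missing rate has no source. The 5% in SAP 4 is overall dropout, a different group, many of whom would have no V7 either. V6 may be done by telephone, video or home visit, so missing V6 and then being seen alive at V7 may be uncommon. This also stands, and the counts are illustrations only.

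Large contradiction rates are tempting too. If both Day 28 items were missing and imputed independently, they would disagree in 2q(1−q) of draws: 42% at q = 0.30 and 50% at q = 0.45. These are full-independence worst cases for subjects whose vital status is unknown, contrary to the joint-model wording, and they do not estimate what the plan would produce.

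Finally, the SAP does not say that the scale is imputed under 8.3.2. SAP 8.3 names predictive mean matching generally, and change in status is tested by rank-ANCOVA, so 8.3.1 might apply. Predictive mean matching can also borrow a Death value from a donor, so the gap remains under either reading.

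**Conclusion.** The concern holds as a missing consistency rule. As written, the SAP permits a Death draw for a subject known to be alive at the target day, and permits imputed mortality and status to contradict each other. The reach is limited to the ordinal secondary endpoints at Days 14 and 28.

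The size is modest. With vital status left out of the model and an assumed 5% of survivors missing only V6, about 4 of about 12 known survivors are set to Death per dataset, and category 6 or higher is understated by 0.8 to 1.0 point per arm. With Day 28 vital status in the model, the Day 28 effect nearly vanishes and about 1 in 20 remains at Day 14. These figures rest on an assumed missing rate and assumed category distributions.

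A reader might infer that the primary result is compromised. The documents do not support that: Day 28 mortality is analysed as its own variable and needs no imputation where vital status is observed. The case for change is that the rule is cheap, removes impossible values, and concerns the endpoints listed first in the secondary order.

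**What to change.** Add to SAP 8.3.2:

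1. Category 1 is assigned only from a recorded or imputed death, never drawn by the status model.
2. Vital status is imputed first, and only where it is unknown. A subject recorded alive on or after a target day is alive on that day, and death is absorbing across Days 14, 28 and 42.
3. Missing clinical status is then imputed among categories 2 to 7, only for subjects alive at the target day, whether the logistic or the predictive mean matching route is used.
4. The mortality endpoints, category 6 or higher, and change in status are all derived from the same completed datasets.

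The cost is a paragraph of SAP text and slightly more imputation programming before unblinding. It needs no extra data and does not change the sample size.

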## 8.4 Multiple Comparisons and Type I Error Rate Multiplicity adjustments

For the primary endpoint only one hypothesis will be tested, the final p-value will be adjusted as specified in Section 5.7 to protect the trial wise Type I error due to the interim analysis.

For the secondary endpoints, the hierarchical test procedure, with fixed sequence approach will be used to protect the trial-wise error rate. Please see Section 9.2.2 for the order of the secondary endpoints.

## 8.5 Subgroups

Subgroup analyses will be conducted to evaluate whether the treatment effects are consistent across different subgroups as following. All subgroup analyses will be considered exploratory, except for some that were prespecified in the protocol for specific reasons.

- 1. Based on baseline Ordinal Scale
- Baseline ordinal scale of Score 2 Critical patients;
- Baseline ordinal scale of Score 3 Severe patients;
- Baseline ordinal scale of Score 4 Severe patients;
- Baseline ordinal scale of Score 3 and 4 Severe patients;
- 2. Based on age group
- Age < 40
- 40 <= Age <= 65
- Age > 65
- 3. Based on Dexamethasone use
- 4. Laboratory parameters such as, CD4/CD8 ratio and IL-6

In addition, the study allowed co-administration of any off-label COVID-19 treatments. Hence, subgroup analyses will be performed to evaluate whether the treatment effects are consistent without and with the different co-administered off-label treatments including but not limited to hydroxychloroquine or chloroquine with or without azithromycin, remdesivir, dexamethasone (or other corticosteroids), monoclonal antibodies (such as bamlanivimab, casirivimab, imdevimab, siltuximab), immunomodulatory agents (such as baricitinib, sarilumab, clazakizumab, tocilizumab, anakinra), convalescent plasma therapy.

#### 8.6 Sensitivity Analysis

Sensitivity analysis is planned for the primary and secondary efficacy endpoints, based on mITT population. Sensitivity analyses will be conducted to assess the impact of potential deviations about the mechanism of missing data assumption in the primary and secondary analysis and the robustness of the primary and secondary analysis.

#### 8.7 Standard Calculations and Conventions

#### 8.7.1 Age

Age will be calculated as the number of completed years between the date of informed consent and the subject's birth date.

Age (years) = integer of 
$$[(date of informed consent - date of birth)/365.25]$$

#### 8.7.2 Body Mass Index (BMI)

BMI will be calculated using height (in cm) and weight (in kg) according to the formula noted below.

BMI 
$$(kg/m^2)$$
 = weight  $(kg) / [[height (cm)/100]^2]$ 

## 8.7.3 Change from Baseline

For any of the effectiveness measurements change from baseline will be calculated using the formula noted below.

#### 8.7.4 Censoring rule for subjects with outcome of Death

For analyses of length of stay (i.e., ICU or hospitalization) or duration of mechanical ventilation all deaths within 42 days will be considered censored at Day 42. Conceptually, a death corresponds to an infinite length of stay or MV support but censoring at any time greater than or equal to Day 42 gives the same answer as censoring at Day 42; both correspond to giving deaths the worst rank.

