During visits conducted at the subject's home, the visiting nurse (or trained site staff) will administer study drug (if applicable), monitor subjects for safety, perform blood draw, and all other assessments related to study outcomes measures. All procedures (except chest radiograph or CT scan) listed under the schedule of assessments can be performed by visiting nurse at visits taking place in the subject's home.

CONFIDENTIAL Page 50 of 108

[figure not shown]

Table 4-2: Schedule of Assessments

Procedure/Assessments	Screening Visit	Treatment Phase				Follow-Up		
Visit	V1	V2 (Pre-Rx)	[17] (Post-Rx)	V3	V4	V5 (EOT)	V6	V 7
Day		Da	y 0	Day 3	Day 7	Day 14	Day 28	Day 42
Window Period			of the Screening sit	3(±1) days after V2	7(±1) days after V2	7(±1) days after V4	14(±3) days after EOT Visit	28(±3) days after EOT Visit
Informed Consent [1]	X							
Eligibility Evaluation [2]	X							
Subject Demographics	X							
Medical History [3]	X							
Physical Examination	X	X		X[4]	X[4]	X	X[4]	X [4]
Vital Signs [5]	X	X	X	X	X	X	X	X
Clinical Status - Ordinal Scale Assessment	X	X		X	X	X	X	
PaO2/FiO2, if intubated	X	X		X	X	X		
Pulse oxygen saturation (SpO2)	X	X		X	X	X		
Positive End-Expiratory Pressure (PEEP), if intubated	X	X		X	X	X		
Sequential Organ Failure Assessment (SOFA) score, if intubated [6]		X		X	X	X		
National Early Warning Score 2 (NEWS2) Assessment [7] [19]	X	X		X	X	X		
Assessment of clinical recovery [8]				X	X	X		
ECG	X					X		
Laboratory tests:								
Complete Blood Count [9]	X			X	X	X		X
Biochemistry [10]	X			X	X	X		X
Coagulation Indices [11]	X			X	X	X		X

CONFIDENTIAL Page 51 of 108

Procedure/Assessments	Screening Visit	Treatment Phase					Follow-Up	
Visit	V1	V2 (Pre-Rx)	[17] (Post-Rx)	V3	V4	V5 (EOT)	V6	V 7
Day		Da	y 0	Day 3	Day 7	Day 14	Day 28	Day 42
Window Period			of the Screening	3(±1) days after V2	7(±1) days after V2	7(±1) days after V4	14(±3) days after EOT Visit	28(±3) days after EOT Visit
Serum/Urine Pregnancy Test [12]	X					X		
Urinalysis [13]	X			X	X	X		X
CD3+, CD4+ and CD8+ T cell count		X		X	X	X		
CCR5 receptor occupancy for Treg and macrophage [19]		X		X	X	X		
Serum cytokine and chemokine levels [19]		X		X	X	X		
CCR5 Gene Polymorphisms [14] [19]		X		X	X	X		
Nasopharyngeal Swab Sample Collection [15] [19]	X	X		X	X	X	X	X
Chest radiograph or CT (if clinically indicated) [16]	X					X		
Randomization [18] [19]		X						
PRO 140 (700 mg) [or Placebo[19]] Administration		2	Υ .		X			

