# 9.2.2.4 Length of hospital stay (days)

Length of hospital stays will be considered as continuous outcome and summarized descriptively.

The median length of hospital stay will be compared between the treatment groups using a non-parametric method or a rank-ANCOVA analysis i.e., an ANCOVA analysis on rank-transformed data. For this analysis, the censoring rule in Section 8.6.4 will be used.

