## 9.2.3.8 Length of ICU stay (days)

Length of ICU stay will be summarized descriptively and compared using ANCOVA adjusting for stratification factors.

If the Normality assumption is not met, a non-parametric method or a rank –ANCOVA analysis i.e., an ANCOVA analysis on rank-transformed data will be used.

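### SAP 8.7.4 says that deaths placed at Day 42 or later take the worst rank and give the same answer; in the planned rank test of hospital stay this holds only if every survivor's value is below 42

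*SAP*

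**What the plan says.** SAP 8.7.4 covers length of stay (hospital or ICU) and duration of mechanical ventilation. Every death within 42 days is set to Day 42. The section justifies this by saying that "censoring at any time greater than or equal to Day 42 gives the same answer as censoring at Day 42" and that "both correspond to giving deaths the worst rank".

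SAP 9.2.2.4 applies the rule to a secondary endpoint: "Length of hospital stays will be considered as continuous outcome and summarized descriptively". The comparison is by a "non-parametric method or a rank-ANCOVA analysis", and the section adds: "For this analysis, the censoring rule in Section 8.6.4 will be used". The SAP has no Section 8.6.4; the rule stands in 8.7.4.

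SAP 8.4 protects the secondary endpoints by a fixed sequence: "Please see Section 9.2.2 for the order of the secondary endpoints". Length of hospital stay comes last there. Neither document gives a start day or a maximum for the stay, or a rule for survivors who have not been discharged. Day 0 is defined as randomization/first treatment in a note under the primary endpoint (SAP 3.1, Protocol 8.2.1).

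**The concern.** The stated aim of the rule is that death counts as the worst outcome. In a rank test a value counts only through its order and its ties. Placing deaths at 42 puts them strictly last only if no survivor has a value of 42 or more. Patients with severe or critical COVID-19 can still be in hospital six weeks after randomization. If they are, the rule does not rank deaths worst, and the choice between 42 and a later value changes the result although the SAP says it does not. At stake are the reported length-of-stay comparison and its nominal p-value, together with a scoring choice that the SAP leaves open because it regards it as immaterial.

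**Working it through.** **Inputs.** Deaths at Day 42 (SAP 8.7.4). Rank-based comparison (SAP 9.2.2.4). Planned numbers 260 and 130, and planning mortality 30% and 45% (SAP 4). The documents give no distribution of stay, so that part is assumed.

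**1. Where the SAP's statement is true.** Take four survivors and two deaths. With survivors at 5, 10, 20 and 41, each death has rank 5.5 whether deaths are placed at 42, 43, 48 or 1000. Under this condition the SAP is right.

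**2. Where it fails.**

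| Survivors | Deaths at | Rank of longest-stay survivor | Rank of each death |
|---|---|---|---|
| 5, 10, 20, 42 | 42 | 5 | 5 |
| 5, 10, 20, 42 | 43 or later | 4 | 5.5 |
| 5, 10, 20, 45 | 42 | 6 | 4.5 |
| 5, 10, 20, 45 | 46 or later | 4 | 5.5 |

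One survivor at 42 already breaks both statements. One at 45 ranks worse than the deaths.

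**3. A cap at 42 alone does not restore it.** One simulated data set (260/130, deaths 37% and 45%, 10% of survivors with stays of 42 to 47 days), regression on ranks:
- survivors capped at 41: t = -1.476 for deaths at 42, 48 or 1,000,000;
- survivors capped at 42: t = -1.375 (p = 0.170) with deaths at 42, and -1.478 (p = 0.140) with deaths at 48.

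Deaths must lie strictly above the largest survivor value.

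**4. Illustrative size.** Assumptions: exponential stay from randomization, rounded up to whole days; placebo median 8, 14 or 20 days; survivors capped at 42; two-sided two-sample t-test on ranks without covariates.

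Expected survivors: 260 × 0.70 + 130 × 0.55 = 253.5. With no discharge effect, the number with a stay of 42 or more is 253.5 × 0.5^(41/median) = 7.3, 33.3 and 61.2. These tie with the deaths when deaths are at 42.

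| Mortality, leronlimab/placebo | Discharge-rate ratio | Power, deaths at 42 (medians 8/14/20) | Power, deaths at 43 |
|---|---|---|---|
| 30/45% | 1.0 | about 68/61/52% | about 70/71/70% |
| 30/45% | 1.4 | about 95/96/95% | about 95/95/94% |
| 35/35% | 1.8 | about 56/68/76% | about 51/50/50% |
| 35/35% | 1.0 (null) | about 5% | about 5% |

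Repeated runs with 3,000 to 6,000 trials per scenario agree within about 2 points.

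**5. With the fixed sequence.** Length of stay is counted as significant only if the primary endpoint and the category-6-or-higher proportions at Days 14 and 28 are significant first. These gates use unadjusted z-tests, and a survivor discharged by that day counts as category 6 or higher. The two endpoints in between are left out, so the true gate is stricter.

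| Scenario | Gated power, deaths at 42 | Gated power, deaths at 43 |
|---|---|---|
| 30/45%, ratio 1.0 | 46.7/27.4/18.3% | 47.0/27.4/18.4% |
| 30/45%, ratio 1.4 | 80.7/76.5/69.0% | 80.7/76.5/69.0% |
| 35/35%, ratio 1.8 | 2.6/2.6/2.8% | 2.6/2.6/2.7% |

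The largest change is 47.0 - 46.7 = 0.3 points.

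**6. Log-rank comparison.** With every subject censored at Day 42, placing deaths at 42 or at 1000 gave the identical statistic in 7,200 of 7,200 simulated trials. In that analysis the SAP's sentence is correct.

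**The case against.** The strongest defence is that the SAP means a 42-day horizon from Day 0. The section is headed as a censoring rule, Day 42 is the nominal last visit, and a non-parametric method could be a log-rank test. Much of this is reasonable, and under a log-rank test with common censoring at Day 42 the sentence stands. But SAP 9.2.2.4 calls the stay a continuous outcome and names rank-ANCOVA, and neither document states censoring of survivors. A 42-day horizon also leaves survivors still in hospital tied with deaths placed at 42.

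A second defence is that hospital stay is scheduled for assessment only up to V5 (Protocol 7.20 and Table 4-2). If only those records were used, counted from Day 0, survivors' values would end by about Day 16 and the sentence would hold. This is correct, but the SAP does not set that cut-off.

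Three stronger readings are tempting and are not supported:
- V7 is scheduled "28(±3) days after EOT Visit", which with the earlier windows gives Day 37 to 47. This does not show that stays above 42 will be recorded, because V7 collects neither hospital stay nor ordinal status. It shows only that follow-up can pass Day 42.
- A stay counted from admission would reach 42 earlier. That start day is a possible reading, which the documents do not state.
- For ICU stay and ventilation, ANCOVA on days is the first choice (SAP 9.2.3.8 and 9.2.3.9), so the value given to deaths would enter the mean. This is hypothetical: the SAP fixes that value at 42, both endpoints are exploratory, and they move to a non-parametric or rank analysis if Normality fails.

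The wrong section number is harmless in itself, since the SAP has only one such censoring rule.

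**Conclusion.** Wrong as written, minor. For the rank comparison in SAP 9.2.2.4, the claims in SAP 8.7.4 about the same answer and the worst rank need every survivor's value to be strictly below 42, and the SAP does not ensure this. That conclusion follows from the ranking itself and needs no assumption about the data.

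The size does need assumptions. With exponential stays and no discharge effect, moving deaths from 42 to 43 raises ungated power by about 2, 10 and 18 points at medians of 8, 14 and 20 days. With equal mortality and a discharge-rate ratio of 1.8 it lowers power by about 5, 18 and 26 points. With the planning mortality and a ratio of 1.4 it hardly matters. After gating, the change is at most about 0.3 points.

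A reader might infer that the secondary testing is invalid or that a formal claim is at risk. Neither follows: rejection under the null stays near 5% with either scoring, and the primary endpoint does not use the rule. What is affected is the reported length-of-stay comparison and its nominal p-value.

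**What to change.** Before unblinding, amend SAP 8.7.4 to count days from randomization (Day 0), cap survivors at 42, and score deaths strictly above the cap, for example at 43, before ranking. Delete the sentence on the same answer. Alternatively, specify a log-rank analysis with all subjects censored at Day 42, in which case the sentence is true. In SAP 9.2.2.4, change 8.6.4 to 8.7.4. Because scheduled assessment of hospital stay ends at V5, also name the source of discharge dates up to Day 42.

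The cost is two or three SAP sentences and one cross-reference, with no change to sample size or visits. If later discharge dates are not already collected, they would have to come from the medical record, which Protocol 14.1 names as the primary source. With no discharge effect this concerns about 254 × 0.5^(14/median) = 75, 127 or 156 survivors at medians of 8, 14 or 20 days. The statistical downside is the lower ungated power when mortality is equal and only discharge is faster. That is the price of ranking deaths worst, as the SAP intends.
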